5.3.5 Management of Immune-Related Toxicities

Treatment of immune-related adverse events (irAEs) should follow guidelines set forth in the following tables. Also, please refer to Appendix B for details.

Table 6. Dose Modification and Management of irAEs

Gastrointestinal irAEs (e.g. diarrhea, colitis)		
Observation	Management	Follow-up
Grade 1 AE	Continue nivolumab therapy. Consider symptomatic treatment (e.g. loperamide, hydration, electrolyte replacement).	Close monitoring for worsening symptoms. Educate patient to report worsening immediately. If worsens: Treat as Grade 2 or 3/4
Grade 2 AE	Delay nivolumab therapy. Symptomatic treatment.	If improves to Grade 1: Resume nivolumab therapy. If no improvement within 5-7 days or recur: Consider starting IV methylprednisolone 0.5-1.0 mg/kg/day or oral equivalent. Once improving, taper steroids over ≥ 1 month and consider prophylactic antimicrobials for opportunistic infections, and consider resuming nivolumab. If the event is not responsive within 3-5 days or worsens despite steroid: Treat as Grade 3/4.
Grade 3 to 4 AE	Discontinue nivolumab therapy. 1.0 to 2.0 mg/kg/day methylprednisolone IV or equivalent. Consider urgent GI consult and imaging and/or colonoscopy as appropriate.	Once improving, taper steroids over ≥ 1 month and consider prophylactic antimicrobials for opportunistic infections. If still no improvement within 3-5 days or recurs after improvement despite steroid: consider adding further immunosuppressives (e.g. infliximab at 5mg/kg once every 2 weeks if no contraindication). Caution: Consider GI

		consult to rule out bowel perforation and refer to infliximab label for general guidance before using infliximab. Infliximab should not be used in cases of perforation or sepsis.
--	--	--

Dermatological irAEs		
Observation	Management	Follow-up
Grade 1-2 AE	Symptomatic therapy (e.g. oral antihistamines, topical steroids). Continue nivolumab therapy.	If persists > 1-2 weeks or recurs: Consider delaying nivolumab. Consider skin biopsy. Consider 0.5-1.0 mg/kg/day methylprednisolone IV or oral equivalent. Once improving, taper steroids over \geq 1 month, consider prophylactic antimicrobials for opportunistic infections, and resume nivolumab. If worsens: Treat as Grade 3-4.

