Grade 3-4 AE	Delay or discontinue nivolumab therapy. 1.0 to 2.0 mg/kg/day methylprednisolone IV or equivalent. Consider dermatology consult and/or skin biopsy.	If improves to Grade 1: taper steroids over \geq 1 month and consider prophylactic antimicrobials for opportunistic infections and consider resuming nivolumab.

Pulmonary irAEs		
Observation	Management	Follow-up
Grade 1 AE	Consider delay of nivolumab therapy. Monitor for symptoms at least every 2-3 days.	Re-image at least every 3 weeks. If worsens: Treat as Grade 2 or Grade 3-4.

	Consider Pulmonary and Infectious Disease consults.	
Grade 2 AE	
Delay nivolumab therapy.
 
Consider Pulmonary and Infectious Disease consults.
 
Monitor symptoms daily, consider hospitalization.
 
1.0 mg/kg/day methyl-prednisolone IV or oral equivalent.
 
Consider bronchoscopy, lung biopsy.
	
Re-image every 1-3 days.
 
If improves: When symptoms return to near baseline, taper steroids over ≥ 1 month, resume nivolumab therapy, and consider prophylactic antimicrobials.
 
If not improving after 2 weeks or worsening: Treat as Grade 3 to 4.

Grade 3 or 4 AE	
Discontinue nivolumab therapy.
 
Hospitalize.
 
Pulmonary and Infectious Disease consults.
 
2 to 4 mg/kg/day methylprednisolone IV or IV equivalent.
 
Add prophylactic microbials for opportunistic infections.
 
Consider bronchoscopy, lung biopsy.
	
If improves to baseline: Taper steroids over at least 6 weeks.
 
If not improving within 48 hours or worsening: Add additional immunosuppression (e.g. infliximab, cyclosporine, tacrolimus, cyclophosphamide, intravenous immunoglobulin, or mycophenolate mofetil).

Hepatic irAEs		
Observation	Management	Follow-up
Grade 1 AE	Continue nivolumab therapy.	Continue liver function monitoring. If worsens: Treat as Grade 2 or 3-4.
Grade 2 AE	
Delay nivolumab therapy.
 
Regular and frequent checking (e.g. every 3 days) of LFTs until elevations of these are improving or resolved.
	If returns to baseline: Resume routine monitoring, resume nivolumab therapy.

		If elevations persist > 5-7 days or worsen: 0.5 to 1 mg/kg/day methylprednisolone or oral equivalent and when LFT returns to Grade 1 or baseline, taper steroids over \geq 1 month, consider prophylactic antimicrobials for opportunistic infections, and resume nivolumab therapy.

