Grade 3 to 4 AE	
Discontinue nivolumab therapy*
 
Regular and frequent checking of LFTs (e.g. every 1-2 days) until elevations of these are improving or resolved.
 
1.0 to 2.0 mg/kg/day methylprednisolone IV or IV equivalent**
 
Add prophylactic antimicrobials for opportunistic infections.
 
Consult gastroenterologist.
	
If returns to Grade 2 or better: Taper steroids over \geq 1 month.
 
If does not improve in > 3 to 5 days, worsens or rebounds: Add mycophenolate mofetil 1 gram (g) twice daily. If no response within an additional 3 to 5 days, consider other immunosuppressants per local guidelines.

*Nivolumab therapy may be delayed rather than discontinued if AST/ALT \leq 8 x ULN and Total bilirubin \leq 5 x ULN.

**The recommended starting dose for grade 4 hepatitis is 2 mg/kg/day methylprednisolone IV.

Endocrine irAEs		
Endocrine Disorder	Management	Follow-up
Asymptomatic TSH elevation	
Continue nivolumab therapy.
 
If TSH < 0.5 x LLN, or TSH > 2 x ULN, or consistently out of range in 2 subsequent measurements: include free T4 at subsequent cycles as clinically indicated; consider endocrinology consult.
	
Symptomatic endocrinopathy	
Evaluate endocrine function.
 
Consider pituitary scan.
	
If improves (with or without hormone replacement): Taper steroids over \geq 1 month and consider prophylactic antimicrobials for opportunistic infections.
 
Resume nivolumab therapy.

	
Symptomatic with abnormal lab / pituitary scan: Delay nivolumab therapy. 1 to 2 mg/kg/day methylprednisolone IV or by mouth equivalent. Initiate appropriate hormone therapy.
 
No abnormal lab / pituitary MRI scan but symptoms persist: Repeat labs in 1 to 3 weeks / MRI in 1 month
	
Subjects with adrenal insufficiency may need to continue steroids with mineralocorticoid component.

Suspicion of adrenal crisis (e.g. severe dehydration, hypotension, shock out of proportion to current illness)
	
Delay or discontinue nivolumab therapy.
 
Rule out sepsis.
 
Stress dose of IV steroids with mineralocorticoid activity.
 
IV fluids.
 
Consult endocrinologist.
 
If adrenal crisis ruled out, then treat as above for symptomatic endocrinopathy.
	

Renal irAEs		
Observation	Management	Follow-up

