5.5 Off-treatment criteria

Treatment may continue until one of the following criteria applies:

- Disease progression and investigator determination that the subject is no longer benefiting from study treatment*
- Any AE that meets criteria for discontinuation as defined in section 5.3.
- Patient decides to withdraw from the study.
- General or specific changes in the patient's condition render the patient unfit for further treatment in the judgment of the investigator.
- Patient is non-compliant with the protocol guidelines.

* Patients are allowed to stay on treatment beyond progression if the investigator thinks that the patient is still benefiting from the treatment.

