****Potential Drug Induced Liver Injury**

Wherever possible, timely confirmation of initial liver-related laboratory abnormalities should occur prior to the reporting of a potential DILI event. All occurrences of potential DILIs, meeting the defined criteria, must be reported as potential drug induced liver injury is defined as:

1) ALT or AST elevation > 3 times upper limit of normal (ULN)

AND

2) Total bilirubin > 2 times ULN, without initial findings of cholestasis (elevated serum alkaline phosphatase)

AND

3) No other immediately apparent possible causes of AST/ALT elevation and hyperbilirubinemia, including, but not limited to, viral hepatitis, pre-existing chronic or acute liver disease, or the administration of other drug(s) known to be hepatotoxic.

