Appendix B. Immune-related toxicity management algorithms.

These general guidelines constitute guidance to the Investigator and may be supplemented by discussions with the Medical Monitor representing the Sponsor. The guidance applies to all immuno-oncology agents and regimens.

A general principle is that differential diagnoses should be diligently evaluated according to standard medical practice. Non-inflammatory etiologies should be considered and appropriately treated.

[figure not shown]
Corticosteroids are a primary therapy for immuno-oncology drug-related adverse events. The oral equivalent of the recommended IV doses may be considered for ambulatory patients with low-grade toxicity. The lower bioavailability of oral corticosteroids should be taken into account when switching to the equivalent dose of oral corticosteroids.

Consultation with a medical or surgical specialist, especially prior to an invasive diagnostic or therapeutic procedure, is recommended.

The frequency and severity of the related adverse events covered by these algorithms will depend on the immuno-oncology agent or regimen being used.

GI Adverse Event Management Algorithm

Rule out non-inflammatory causes. If non-inflammatory cause is identified, treat accordingly and continue I-O therapy. Opiates/narcotics may mask symptoms of perforation. Infliximab should not be used in cases of perforation or sepsis.

Patients on IV steroids may be switched to an equivalent dose of oral corticosteroids (e.g. prednisone) at start of tapering or earlier, once sustained clinical improvement is observed. Lower bioavailability of oral corticosteroids should be taken into account when switching to the equivalent dose of oral corticosteroids.

Updated 05-Jul-2016

Renal Adverse Event Management Algorithm

[figure not shown]
Rule out non-inflammatory causes. If non-inflammatory cause, treat accordingly and continue I-O therapy

Patients on IV steroids may be switched to an equivalent dose of oral corticosteroids (e.g. prednisone) at start of tapering or earlier, once sustained clinical improvement is observed. Lower bioavailability of oral corticosteroids should be taken into account when switching to the equivalent dose of oral corticosteroids.

Pulmonary Adverse Event Management Algorithm

Rule out non-inflammatory causes. If non-inflammatory cause, treat accordingly and continue I-O therapy. Evaluate with imaging and pulmonary consultation.

[figure not shown]

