Patients on IV steroids may be switched to an equivalent dose of oral corticosteroids (e.g. prednisone) at start of tapering or earlier, once sustained clinical improvement is observed. Lower bioavailability of oral corticosteroids should be taken into account when switching to the equivalent dose of oral corticosteroids.

Updated 05-Jul-2016

Hepatic Adverse Event Management Algorithm

Rule out non-inflammatory causes. If non-inflammatory cause, treat accordingly and continue I-O therapy. Consider imaging for obstruction.

[figure not shown]
Patients on IV steroids may be switched to an equivalent dose of oral corticosteroids (e.g. prednisone) at start of tapering or earlier, once sustained clinical improvement is observed. Lower bioavailability of oral corticosteroids should be taken into account when switching to the equivalent dose of oral corticosteroids.

*I-O therapy may be delayed rather than discontinued if AST/ALT ≤ 8 x ULN or T.bili ≤ 5 x ULN.

**The recommended starting dose for grade 4 hepatitis is 2 mg/kg/day methylprednisolone IV.

Skin Adverse Event Management Algorithm

Rule out non-inflammatory causes. If non-inflammatory cause, treat accordingly and continue I-O therapy.

[figure not shown]
Patients on IV steroids may be switched to an equivalent dose of oral corticosteroids (e.g. prednisone) at start of tapering or earlier, once sustained clinical improvement is observed. Lower bioavailability of oral corticosteroids should be taken into account when switching to the equivalent dose of oral corticosteroids.

*Refer to NCI CTCAE v4 for term-specific grading criteria.

^If SJS/TEN is suspected, withhold I-O therapy and refer patient for specialized care for assessment and treatment. If SJS or TEN is diagnosed, permanently discontinue I-O therapy.

Neurological Adverse Event Management Algorithm

[figure not shown]
Rule out non-inflammatory causes. If non-inflammatory cause, treat accordingly and continue I-O therapy.

Patients on IV steroids may be switched to an equivalent dose of oral corticosteroids (e.g. prednisone) at start of tapering or earlier, once sustained clinical improvement is observed. Lower bioavailability of oral corticosteroids should be taken into account when switching to the equivalent dose of oral corticosteroids.

Endocrinopathy Management Algorithm

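### Severe hepatic immune-related events: Table 6 requires both liver limits to be met before nivolumab may be delayed instead of discontinued, while Appendix B requires only one

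*Combined protocol and SAP*

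**What the plan says.** Table 6 (Section 5.3.5, hepatic events) tells the site to discontinue nivolumab for a grade 3-4 event. It marks that instruction with an asterisk. The asterisked footnote relaxes discontinuation to delay when AST/ALT is no more than 8 x ULN and total bilirubin is no more than 5 x ULN: "8 x ULN and Total bilirubin".

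The hepatic algorithm in Appendix B carries a footnote with the same purpose and the same limits, but a different connector: "8 x ULN or T.bili".

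Four other places bear on which text applies:

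- Section 5.3.5 says that treatment of immune-related events "should follow guidelines set forth in the following tables. Also, please refer to Appendix B for details".
- Section 5.5 ends treatment for "Any AE that meets criteria for discontinuation as defined in section 5.3" and does not name Appendix B.
- Section 12.5 requires the study to be run exactly as the approved protocol describes, emergencies aside.
- The introduction to Appendix B says "These general guidelines constitute guidance to the Investigator", and that the guidance covers immuno-oncology agents in general.

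**The concern.** One word changes the rule. Under *and*, a single value above its limit is enough to require discontinuation. Under *or*, discontinuation is required only when both values exceed their limits. Read that way, the AST/ALT limit does nothing while bilirubin is within 5 x ULN, and the bilirubin limit does nothing while AST/ALT is within 8 x ULN.

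A site working from Appendix B could therefore keep a patient eligible for further nivolumab whom Table 6 would take off it permanently. Section 11.2 plans for up to seven institutions, so sites could apply the rule differently. A monitor who finds a delay under the Appendix B wording would have no clear text by which to call it a deviation.

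**Working it through.** No sample-size or error-rate figure is involved. The check is a comparison of two logical conditions.

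**Inputs.** Let A mean AST/ALT ≤ 8 x ULN, and B mean total bilirubin ≤ 5 x ULN. Both limits stand in both footnotes.

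- Table 6 permits delay if A **and** B.
- Appendix B permits delay if A **or** B.

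**All four combinations.**

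| A (AST/ALT ≤ 8 x) | B (bilirubin ≤ 5 x) | Table 6 | Appendix B | Differ? |
|---|---|---|---|---|
| yes | yes | delay permitted | delay permitted | no |
| no | yes | discontinue | delay permitted | yes |
| yes | no | discontinue | delay permitted | yes |
| no | no | discontinue | discontinue | no |

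The rules differ in two of four combinations, and in both Appendix B is the more permissive.

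**Illustrative values.** These are assumed. The documents give no grading cut-offs for liver tests, so each is taken to be a grade 3-4 immune-related event for the sake of the example. The last column applies only the laboratory limits of the potential drug-induced liver injury definition in Section 8.1.4 (ALT or AST > 3 x ULN, with "Total bilirubin > 2 times ULN, without initial findings of cholestasis"). It asks whether that definition would catch the discordant cases.

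| AST/ALT (x ULN) | Bilirubin (x ULN) | Table 6 | Appendix B | Differ? | Liver-injury laboratory limits exceeded? |
|---|---|---|---|---|---|
| 6 | 2 | delay | delay | no | no (2 is not > 2) |
| 15 | 2 | discontinue | delay | yes | no (2 is not > 2) |
| 15 | 4 | discontinue | delay | yes | yes |
| 25 | 4 | discontinue | delay | yes | yes |
| 6 | 6 | discontinue | delay | yes | yes |
| 2.5 | 6 | discontinue | delay | yes | no (2.5 is not > 3) |
| 15 | 6 | discontinue | discontinue | no | yes |

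Five of the seven examples are discordant, and the liver-injury limits are exceeded in three of those five. Where they are, and the other parts of the definition are met, the event is a serious adverse event that Section 8.3 requires to be reported within 24 hours. That is a reporting duty and does not require discontinuation.

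**Other safeguards.** A footnote to the table for other immune-related events requires permanent discontinuation in two situations: steroids cannot be reduced to 10 mg prednisone or less per day within 12 weeks, or a grade 3 treatment-related event recurs after dosing resumes. It is attached to the grade 3 row of that table, so applying it to hepatic events is an assumption. Its recurrence limb acts only after re-exposure.

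**Does it reach the trial's results?** Under Section 5.1.1.1 a related grade 3 or 4 hepatic toxicity in the first cycle is a DLT whichever footnote is followed; hepatic events are not among the listed exclusions. Neither footnote enters the definition or analysis of PFS, the event count or the significance level.

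**The case against.** **The protocol already points to Table 6.** Section 5.3.5 says to follow the tables, Section 5.5 ties stopping to Section 5.3, Section 12.5 demands exact adherence, and Appendix B presents itself as general guidance. On an ordinary reading the trial-specific table prevails. This stands as a strong indication, but it is not a stated rule. Section 5.3.5 also sends the reader to Appendix B for detail, and the delay limits are just that kind of detail.

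**The *or* may be loose drafting.** It could mean that each limit applies to whichever test drives the event. AST/ALT of 15 x ULN with bilirubin of 2 x ULN would then lead to discontinuation under both texts. That may be what was intended, but the words do not say it. The divergence shown above is the literal reading and an upper bound on what sites would do.

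**The flowchart is not shown.** The box marked by the Appendix B asterisk cannot be seen. It is inferred from the matching limits, the near-identical wording and the identical second footnote on the steroid dose for grade 4 hepatitis. The inference is strong but not verified.

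**Some examples may be out of scope.** Appendix B first asks the site to rule out non-inflammatory causes and to consider imaging for obstruction. A mainly bilirubin-driven case, such as 2.5 x with 6 x, may not be immune-related at all. This is fair, but it does not touch the AST/ALT-driven cases.

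**A wider conflict might be inferred.** A reader might conclude that Table 6 and Appendix B clash across organ systems and that a general rule of precedence is needed. The documents do not show this. For severe skin events, for instance, Table 6 allows delay or discontinuation, and Appendix B names diagnoses for which discontinuation is required; that is added detail, not contradiction. A sentence saying that the stricter text applies would also be undefined for steroid dose and taper, and would reach organ systems whose flowcharts are not shown.

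**Conclusion.** The inconsistency is real and stands in the current text. With exactly one of the two liver limits exceeded, Table 6 requires discontinuation and Appendix B, taken literally, permits delay.

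Its effect is limited to whether a few patients remain eligible for re-exposure to nivolumab. The number cannot be estimated from the documents.

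A reader might infer that Appendix B lets nivolumab continue through severe hepatitis, or that dose finding or the efficacy comparison is compromised. Neither follows. Nivolumab is interrupted at once under either footnote, both footnotes are permissive, and Table 6's monitoring, steroid and consultation steps do not depend on the choice. DLT counts, the recommended phase II dose, PFS, power and alpha are unaffected.

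The conclusion rests on reading *or* literally and on the inference that the Appendix B asterisk marks the grade 3-4 discontinuation box.

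**What to change.** In the Appendix B hepatic footnote, change *or* to *and* so that it matches Table 6. When doing so, the sponsor should confirm on the full flowchart that the asterisk marks the grade 3-4 discontinuation box. No other change is needed.

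The cost is one word. Section 12.6 requires a written amendment with IRB approval before implementation, so the correction can travel with the next amendment. The only downside is that a few patients with one value above its limit lose the option of delay, which Table 6 already denies them.

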5.4 Concomitant Medications/Treatments

Concomitant use of chemotherapy or investigational agents are not allowed. Palliative radiation to limited areas is allowed during the study, unless this is required because of progression of the disease.

5.5 Off-treatment criteria

Treatment may continue until one of the following criteria applies:

- Disease progression and investigator determination that the subject is no longer benefiting from study treatment*
- Any AE that meets criteria for discontinuation as defined in section 5.3.
- Patient decides to withdraw from the study.
- General or specific changes in the patient's condition render the patient unfit for further treatment in the judgment of the investigator.
- Patient is non-compliant with the protocol guidelines.

* Patients are allowed to stay on treatment beyond progression if the investigator thinks that the patient is still benefiting from the treatment.

5.6 Off-study criteria

- Death
- Patient decides to withdraw consent from the study.
- Lost to follow-up

- Completed study follow-up period
- Investigator discretion

5.7 Duration of Follow-Up

Patients will be followed either with clinic visits or phone interviews yearly for two years. Patients removed from treatment for unacceptable adverse event(s) will be followed clinically until resolution or stabilization of the adverse event, and then via clinic visits or phone interviews yearly for two years.

The following information will be collected:

- Date of follow up
- Is patient dead or alive?
- If dead, document exact date of death.
- Further treatment(s), if any
- Document date of disease progression

6.0 STUDY PROCEDURES

6.1 Screening/Baseline Procedures

Subjects who meet all eligibility criteria will be enrolled in the study. Assessments performed exclusively to determine eligibility for this study will be done after obtaining informed consent. Assessments performed for clinical indications (not exclusively to determine study eligibility) may be used for baseline values even if the studies were done before informed consent was obtained. All screening procedures must be performed within 4 weeks prior to starting study drugs, unless otherwise stated. The screening procedures include:

- Complete history and physical examination including vital signs, height, weight and ECOG performance score (see appendix C).
- Baseline imaging studies: Patients should have a baseline radiographical evaluation with computed tomography (CT) scan of the chest/abdomen/pelvis, MRI or CT of the brain, and FDG-PET (skull base to mid-thigh). Two NETSPOT[®] PET scans will be performed, the first one within 4 weeks before the start of chemotherapy (preferable) or as soon as possible after initiation of chemotherapy. This scan will be used to evaluate SSTR2 expression and the patient's eligibility for the study. The second NETSPOT[®] PET scan will be conducted as far as possible from the end of chemotherapy (ideally within 1 week before the start of study treatment). This scan will be used for exploratory analysis on eventual SSTR2 expression modification with chemotherapy. If a patient presents after completion of chemotherapy and did not have a NETSPOT[®] PET scan performed before or during chemotherapy, a NETSPOT[®] PET scan will be obtained to determine the patient's eligibility. The participating centers of the proposed study will follow the approved reconstitution and quality control procedures for [⁶⁸Ga]-DOTATE, and will use the qualified Ge-68/Ga-68 generator. Outside imaging studies will be accepted at the discretion of the PI.
- Electrocardiogram (EKG)

- Laboratory evaluation (baseline tests to be obtained within two weeks prior to starting treatment unless otherwise noted)
 - Hematological Profile: Complete blood count (CBC) with differential and platelet count, prothrombin time/international normalized ratio (PT/INR), activated partial thromboplastin time (aPTT).
 - Biochemical Profile: Sodium, potassium, calcium, phosphorous, magnesium, blood urea nitrogen (BUN), creatinine, glucose, aspartate aminotransferase (AST), alanine aminotransferase (ALT), alkaline phosphatase, lactic acid dehydrogenase (LDH), bilirubin, albumin.
 - Baseline glomerular filtration rate (GFR) calculation.
 - Serum or urine beta-hCG for female patients of childbearing age within 24 hours prior to the start of study drug.
 - Viral Markers: HBsAg (hepatitis B surface antigen), anti-HCV antibody, anti-HIV antibody within 3 months prior to starting treatment.
 - Amylase, lipase, thyroid function test (TSH, free T3, free T4).

